Recently, we performed a single-center trial investigating the effect of the implementation of the KDIGO bundles to obtain preliminary data. We found a significant decrease in the occurrence of AKI within 72 hours in high risk patients (defined as TIMP-2*IGFBP7≥0.3) undergoing cardiac surgery (55.1% in the intervention versus 71.7% in the control group, p=0.004).

In this feasibility trial we will analyze the compliance rate to the trial protocol in a multicenter, multinational cohort in preparation for a large randomized controlled trial.

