6.1 Endpoints

The primary endpoint of this trial is the compliance rate, i.e. the proportion of patients who have been treated according to the trial protocol(KDIGO recommendations fulfilled at all time).

Secondary endpoints include occurrence of AKI within 72 hours after cardiac surgery, moderate and severe AKI, severity of AKI, renal recovery at days 30,60 and 90, 30-day, 60-day and 90-day mortality, length of ICU stay, length of hospital stay, need and duration of RRT, RRT at days 30, 60 and 90, MAKE₃₀, MAKE₆₀ and MAKE₉₀ (major adverse kidney events consisting of mortality, dialysis dependency persistent renal dysfunction (defined as serum creatinine \geq 2x compared to baseline value).

The randomization ratio is 1:1.

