6.2 Sample size

The required sample size is n=280 patients in total. This sample size is determined as follows.

Patients will be randomized in a 1:1 ratio to one of the two treatment arms (intervention versus control). Randomization serves to estimate the incidence of AKI as secondary outcome to generate pre-information in terms of a pilot study for an upcoming confirmatory trial.

The primary endpoint of the PrevAKI-multicenter trial is the compliance rate, i.e. the proportion of patients who have been treated according to the trial protocol (KDIGO recommendations fulfilled at all time). In order to estimate the compliance rate, the two treatment groups will be pooled together. In the primary analysis the compliance rate across all study patients will be estimated along with a two-sided 95% confidence interval (CI).

As the compliance rate cannot be quantified in advance, we pursue a worst case approach and assume a compliance rate of 50%. In this case the CI has maximal width. Based on this assumption, with a sample size of n=280 patients the calculated 95% CI according to Clopper-Pearson (Fleiss 2003) ranges from 44% to 56%. Therefore, in case of any observed compliance rate apart from the worst-case scenario, the 95% CI is never wider than 56%-44%=12%. This corresponds to an estimation of the compliance rate with a precision of plus/minus 6%.

CONFIDENTIAL

Date: 16.02.2017 Version: V1

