6.3 Statistical analysis plan

The trial is designed to examine the feasibility of the trial protocol in a multicenter setting (as previously described).

The **descriptive analysis** of the data will include the calculation of means, standard deviations, and absolute and relative frequencies of the baseline and follow-up data. Randomization will be checked by suitable two-sided statistical tests (Chi-Square, or Fisher's exact test for categorical data, Students' t-Test or Mann-Whitney-U tests for continuous data). If normality of the data is not given non-parametric methods will be used.

In the primary statistical analysis the compliance rate across all recruited study patients will be estimated along with a two-sided 95% confidence interval (CI)according to Clopper-Pearson (Fleiss 2003).

Secondary endpoints will be analyzed in the ITT collective using Fisher's exact tests or chisquared tests for categorical data, and Student's t-tests or Mann-Whitney-U tests for continuous data. Prognostic risk factors for AKI will be identified using a multivariable logistic regression analysis, accounting for confounding factors. In particular, based on a full model with potentially relevant covariates (e.g. sex, age, previous heart surgery, preoperative creatinine) the final model will be established applying a stepwise variable selection procedure.

7 Use of trial findings

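### Stepwise selection of the AKI risk-factor model overstates the effects it retains, and with many candidates its 95% intervals under-cover; one fixed, short model would serve better

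*Combined protocol and SAP*

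**What the plan says.** Section 6.3 states: "Prognostic risk factors for AKI will be identified using a multivariable logistic regression analysis, accounting for confounding factors". The starting point is a full model whose covariates are given only as examples ("e.g. sex, age, previous heart surgery, preoperative creatinine"), and "the final model will be established applying a stepwise variable selection procedure".

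The plan does not give a closed candidate list, the direction of the procedure, an entry or stay criterion, any shrinkage or validation, or an exploratory label. Treatment arm and centre are not among the examples. The same section analyses the primary endpoint, the pooled compliance rate, by an exact confidence interval and the secondary endpoints by unadjusted two-group tests. Neither uses this model.

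**The concern.** Two things sit badly together. Accounting for confounding means keeping a confounder whatever its p-value, whereas a stepwise rule keeps or drops each variable on how strongly it shows up in this sample. Nothing in the plan protects a confounder, treatment arm or centre from being dropped. Arm is randomised and so does not confound baseline factors, but the trial's hypothesis is that it changes AKI risk. Centre matters because section 2.4 leaves standard care to each centre's routine.

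The second problem is that the surviving terms are estimated on the same data that chose them. A weak factor survives only when its estimate happens to be large, so the published odds ratio is too big on average. Intervals computed as if the model had been fixed in advance ignore the selection. At stake is the credibility of the reported list of AKI risk factors and its odds ratios. Because the settings are open, two analysts following section 6.3 could also report different lists from the same data.

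**Working it through.** **The plan's own figure.** Section 6.2 says that "with a sample size of n=280 patients the calculated 95% CI according to Clopper-Pearson (Fleiss 2003) ranges from 44% to 56"%. The exact interval for 140/280 is 43.99% to 56.01%, width 12.02%, so the figure reproduces. It concerns compliance only; the documents give no figure for the risk-factor model.

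**Inputs from the documents**
- Size: "The required sample size is n=280 patients in total" (section 6.2), and "The randomization ratio is 1:1" (section 6.1).
- AKI rate in the single-centre trial: "55.1% in the intervention versus 71.7% in the control group, p=0.004" (section 2.2). That it carries over is an assumption. Mean (55.1 + 71.7)/2 = 63.4%; 280 × 0.634 ≈ 178 with AKI and 280 − 178 = 102 without.

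**Assumed, because the plan is silent:** 4 to 20 candidates, three of them true with OR 1.4 per SD and the rest noise; independent standard normal covariates; backward elimination at p<0.05.

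**1. Why survivors are inflated.** The standard error of a log OR per SD is roughly 1/√(280 × 0.634 × 0.366) = 1/√64.97 = 0.124. To survive at p<0.05 an estimate must exceed about 1.96 × 0.124 = 0.243, an OR of 1.28. The true value is ln 1.4 = 0.336. The mean of a normal(0.336, 0.124) variable truncated at 0.243 is about 0.385, or 1.14 times the truth. The small-sample bias of logistic regression, 2–10% in the full model, comes on top. Simulation gives 19–22% for 4 to 20 candidates. In odds ratios, a true 1.40 is reported on average as exp(0.336 × 1.19) = 1.49 to exp(0.336 × 1.22) = 1.51, against 1.41 to 1.45 from the full model.

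Sensitivity:
- A true OR of 1.25 has its log OR multiplied by 1.58–1.61 at p<0.05, and by 1.38–1.43 at an AIC-like 0.157.
- A true OR of 1.5 is overstated by 4–11%.
- With covariate correlation 0.3 at p<0.05, the factors are 1.83–1.88 (OR 1.25), 1.20–1.22 (OR 1.5) and 1.06–1.07 (OR 2.0).

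**2. Coverage of the retained intervals.** A noise term kept at p<0.05 has a 95% interval that excludes 1 by construction, so it never covers the truth. Retained true terms cover near the nominal level (92–97% in the uncorrelated runs with OR 1.25 and 1.5 at p<0.05). About 27% of true factors are dropped, so 3 × 0.73 = 2.19 are kept on average. With m noise candidates, about 0.05m are kept, and coverage ≈ 0.95 × 2.19/(2.19 + 0.05m).

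| Candidates (noise, m) | Any noise kept: 1 − 0.95^m | Any noise kept: simulated | Coverage: arithmetic | Coverage: simulated |
|---|---|---|---|---|
| 4 (1) | 5% | about 6% | 0.95 × 2.19/2.24 = 93% | about 95% |
| 8 (5) | 23% | about 24% | 0.95 × 2.19/2.44 = 85% | about 86% |
| 12 (9) | 37% | about 39% | 0.95 × 2.19/2.64 = 79% | about 79% |
| 20 (17) | 58% | about 62% | 0.95 × 2.19/3.04 = 68% | about 66% |

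When every term is reported, full-model intervals cover about 94–95%. The shortfall therefore comes from presenting selected noise terms as findings, not from badly computed intervals for true factors.

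**3. What depends on sample size.** With 10 candidates, true ORs of 1.25 and 1.5 and p<0.05, the multiplier for the OR of 1.25 falls from 1.55 at n=280 to 1.05 at n=1000 and 1.00 at n=3000. The chance of keeping a noise variable is 35%, 34% and 34%.

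**4. Full model read at p<0.05.** With 12 candidates it flags at least one noise variable in 40% of trials against 39% for stepwise, and misses 27% of true factors against 27%.

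**The case against.** The strongest reply is that most of what is usually blamed on stepwise selection is not specific to it. That stands. A reader might infer that a trial of this size makes stepwise selection pick up noise, or that moving to a full model cures this. Neither holds: noise retention follows the number of candidates and the threshold, and a full model read at p<0.05 does no better. A gain comes only from a shorter list and from not sorting variables by p-value.

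The plan names only four covariates, all clinically sensible. If those were the whole list, coverage in the assumed setting would be about nominal and a noise variable would be kept in about 6% of trials if one of the four were noise, or at most about 19% (1 − 0.95^4) if all four were. This stands too, but the list is open, and the visit schedule in section 4.7.1.3 collects many more variables. The inflation of about 19–22% appears even with four candidates.

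A reader might also infer that arm and centre are excluded; a list of examples excludes nothing, so the fair statement is that they are unprotected. Nor do the documents say that the risk-factor list will set the next trial's stratification. Section 6.2 gives estimating AKI incidence as the purpose of randomising, and section 2.4 links adherence to the next power analysis. Finally, the plan does not say that selection is by p-value. An AIC-type rule would inflate less and keep more noise: with two true factors among 10 candidates, 76% at 0.157 against 34% at 0.05.

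**Conclusion.** The point holds in a limited form. Section 6.3 commits to a method that overstates the effects it retains and, once the candidate list grows beyond a handful, yields reported intervals that cover too little. Under the stated assumptions the inflation is about 19–22% on the log scale against 2–10% without selection, and coverage falls from about 95% with 4 candidates to 66% with 20. Inflation is larger for weaker or correlated factors and small for strong ones. The number of candidates, the threshold, the true effects and the AKI rate are all assumed.

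The plan's aim of accounting for confounding is not secured by a procedure free to drop confounders. The consequence is confined to a secondary analysis. A reader might infer that the trial's main results are compromised; they are not, because the compliance estimate and the unadjusted comparisons between arms do not use this model. It is a worthwhile, inexpensive improvement.

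**What to change.** Replace the stepwise step in section 6.3 by one model fixed before database lock, with every term kept whatever its p-value: treatment arm, centre as a random intercept, age, sex, previous heart surgery, preoperative creatinine, CPB time and baseline [TIMP-2]*[IGFBP7]. State that:
- odds ratios with 95% confidence intervals are reported for all terms, and no factor is declared by p<0.05;
- penalised estimation (ridge or Firth) is used if events are sparse;
- the analysis is exploratory.

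The data are already planned: three of the patient covariates are named in section 6.3 together with preoperative creatinine as the fourth, CPB time is in the visit schedule (section 4.7.1.3), and the biomarker is measured for eligibility (section 4.6.1). There are seven fixed terms besides the centre intercept, so the assumed 102 patients without AKI give 102/7 ≈ 14.6 per term.

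The cost is SAP wording, slightly wider intervals and a less parsimonious table. The change removes the inflation due to selection and keeps confounders in. It lowers false leads only because the list is short and p-values are not used to sort it.

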7.1 Publication

It is planned to publish the trial results, in mutual agreement with the PCI, in a scientific journal and at international congresses. Publication of the results of the trial as a whole is intended. Any publication will take account of the International Committee of Medical Journal Editors(ICMJE).

The trial will also be registered in a public register in accordance with the recommendations of the ICMJE.

Any published data will observe data protection legislation covering the trial subject and investigators. Success rates or individual findings at individual trial sites are known only to the responsible institution.

Publications or lectures on the findings of the present clinical trial either as a whole or at individual investigation sites must be approved by the responsible institution in advance, and the

CONFIDENTIAL

Date: 16.02.2017 Version: V1

responsible institution reserves the right to review and comment on such documentation before publication.

8 Costs and payments

8.1 Research study costs

There will be no additional costs to subjects of this study. The additional study costs above what is considered to be standard hospital care are the costs for data management, statistical analysis, measurement of renal biomarkers and laboratory costs. These costs will be covered by the ESICM Trials Group Award given to [name] (Principal Coordinating Investigator). Subjects and their insurers and third party payers will be billed for routine care services, or services not connected with the study. These routine care services include services provided during this hospitalization and any ongoing services or medications required after leaving the hospital. Subjects will be responsible for any applicable copies, coinsurances, and deductibles.

11.3 Scores

SOFA-Score

SOFA Score	SOFA Score 0		2	3	4	
Respiration PaO ₂ /FiO ₂	>400	<400	<300	<200	<100	
Platelet count (10³/µl)	>150	<150	<100	<50	<20	
Bilirubin (mg/dl)	<1.2	1.2-1.9	2.0-5.9	6.0-11.9	>12	
Cardiovascular	No hypotension	MAP <70 mmHg	Dobutamine (any dose)	Norepinephrine/ epinephrine ≤0.1µg/kg/min	Norepinephrine/ epinephrine > 0.1µg/kg/min	
GCS	15	13-14	10-12	6-9	<6	
Creatinine (mg/dl) or UO (ml/d)	<1.2	1.2-1.9	2.0-3.4	3.5-4.9 ≤500	>5.0 <200	

CONFIDENTIAL

Date: 16.02.2017 Version: V1

APACHE-Score

Points	+4	+3	+2	+1	0	+1	+2	+3	+4
Temp. °C	≥41	39-40.9		38.5- 38.9	36-38.4	34-35.9	32-33.9	30-31.9	≤29.9
MAP (mmHg)	≥160	130-159	110- 129		70-109		50-69		≤49
HF/min	≥180	140-179	110- 139		70-109		55-69	40-54	≤39
AF/min*1	≥50	35-49		25-34	12-24	10-11	6-9		≤5
Oxygenation	≥500	350-499	200- 349		71-199	61-70		55-60	<55
pH	≥7.7	7.6-7.69		7.5- 7.59	7.33-7.49		7.25- 7.32	7.15-7.24	<7.15
Na+ (mmol/L)	≥180	160-179	155- 159	150- 154	130-149		120- 129	111-119	≤110
K+ (mmol/L)	≥7	6.6-6.69		5.5- 5.59	3.5-5.4	1.0-3.4	2.5-2.9		≤2.5
Creatinine (mg/dl) *2	≥3.5	2.0-3.4	1.5-1.9		0.6-1.4		<0.6		
Hematocrit (%)	≥60		50-59.9	46-49.9	30 -45.9		20-29.9		<20
Leukocytes (x1000)	≥40		20-39.9	15-19.9	3-14.9		1-2.9		<1
GCS	Points= 15-current GCS								

^{*1} spontaneous breathing or mechanical ventilation *2 AKI receives double points

ASA-Score

ASA I	Normal healthy patients
ASA II	Patients with mild systemic disease
ASA III	Patients with severe systemic disease that is limiting but not incapacitating
ASA IV	Patients with incapacitating disease which is a constant threat to life
ASA V	Moribund patients not expected to live more than 24 hours
ASA VI	A declared brain-dead patient whose organs are being removed for donor purposes

CONFIDENTIAL

Date: 16.02.2017 Version: V1
